#### **PrEP Social Influence Campaign CRT:**

The CRT under current consideration will compare the existing standardized community engagement model (i.e. PrEP sensitization/promotion) to an enhanced PrEP social influence campaign using different delivery mechanisms. **The primary outcome will be the proportion of FSW/AGYW clients within the TB HIV Care PrEP programme who initiate PrEP among all eligible marginalized young women to whom it is offered.** Secondary outcomes will be differences in knowledge, attitudes and peer influence across arms (described in sections below)

and 1 and 4-month sustained PrEP use among PrEP initiators. The enhanced social media campaign will be implemented for 12-months while the PrEP champion and community mobilization interventions will be implemented for 6-months and will target young women, parents, teachers, peers, and partners. 5 TB HIV Care district sites within the four provinces will be randomized to each arm (10 districts randomized in total).

There will be two main study arms which will be randomized 1:1 at the district level across the 10 sites which span four provinces. **Arm 1** will receive PrEP sensitization per the ongoing programmatic Standard of Care. **Arm 2** will receive the standard of care through the programme per normal, as well as an enhanced social media intervention that will be targeted to the intervention districts. This is feasible because through social media platforms like Facebook, advertisements can be geographically targeted to specific areas. The primary outcome of PrEP uptake will be powered to assess the difference in PrEP initiations across the 10 sites, comparing PrEP uptake numbers in Arms 1 and 2. Additionally, a second layer of enhancement will be layered onto the intervention arms (Arm 2). Thus in addition to the social media campaign, wards from the five intervention districts will be randomly selected to implement: a) Nothing additional; b) Training and support for venue-based PrEP champions; c) PrEP community mobilization teams; d) Training and support for venue-based PrEP champions AND PrEP community mobilization teams. Details are further highlighted in Table 1 below:

Table 1: Intervention activities and CRT plan		
Arm	Name	Description

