Arm 1*	Standard of care	Full-time peer educators employed by the programme to engage women, layer PrEP promotion across prevention programs, and implement “refer a friend” strategies, information, education and communication (IEC) materials, service user testimonials, risk reduction posters to increase young women’s perception of risk, working after hours/weekends to reach young women, working with school governing bodies, and door-to-door outreach.
Arm 2*	Enhanced social media campaign	PrEP social influence campaign, which will use online approaches to promote PrEP within communities in addition to the standard of care activities. Messaging crafted with community input will be geographically targeted to women, parents/mentors, and male partners on Facebook and/or Instagram (final platforms to be determined based on marketing research conducted by Community Health Trust who will contracted to manage the campaign), all with the intention to promote PrEP for women at high risk of HIV infection and change community norms and influence around PrEP. A combination of static imagery and brief videos will be used to engage these groups via social media platforms. High profile social influencers may be engaged as faces of the campaign, including for ads and video creation. A Facebook page will be created and maintained that can be accessed by anyone anywhere, but will only be advertised/promoted in the intervention districts.
Arm 2a**	Nothing additional	Wards in Arm 2a will not receive any additional strategies. They will still receive (as will all arms) the standard of care, as well as the enhanced social media campaign received by all wards in Arm 2.

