Arm 2b**	PrEP champions	Within venues served by the FSW and AGYW programs, we will identify and train 1 venue-based PrEP champion per venue who will (a) have completed a 2 day group-based (cross-venue) health information training related to PrEP knowledge, with pre and post testing knowledge assessments to identify knowledge gaps; (b) receive supplies (e.g. a hat, pin and posters, flyers, IEC material) to wear to promote PrEP; (c) facilitate linkage between women interested in PrEP and the TB HIV Care PrEP programme; and (d) receive bi-weekly follow-up support from TB HIV Care to discuss challenges, progress and referrals. A partial day refresher training will be held at 3-months. PrEP champions will be either peers with experience taking PrEP, venue managers or local influencers (e.g. women running shops next to the mobile serving AGYW) that have repeated contact with the women the programme is intended to serve. The final selection of PrEP champions will be made in consultation with the Community Advisory Groups, venues and by the programme who works closely with each of the sites. The PrEP champions will receive a small airtime stipend (R150 per month) to follow-up and provide support to women engaging in PrEP.
Arm 2c**	PrEP community mobilization	A PrEP community mobilization team (2 peers, including one woman and one man) will be recruited within each ward to promote PrEP. The team will present information about PrEP and the PrEP programme at the ward councilors meeting, at Learning Support Agent meetings with parents/guardians, at local events/fairs, community meetings and through engaging men, women and parents across the community through informal conversations. Teams will be wearing branded material and will focus on presenting factual information and decreasing PrEP stigma, and will have received 3 days of training in HIV, PrEP, and health communication and persuasion to promote positive PrEP norms and attitudes within the community, with a 1-day refresher training at 3-months. Each team will focus on promoting PrEP within their own ward over the 6-month period.
Arm 2d**	PrEP champions + PrEP community mobilization	Wards in Arm 2d will receive both of the two additional strategies described above (2b & 2c).

\*10 districts randomized 1:1 across Arms 1 and 2.

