#### *B. Sample Size Considerations*

**Social influence campaign (CRT):** The primary outcome for this study will be PrEP uptake within the TB HIV Care programme. Each of the 10 cities in which TB HIV Care provides PrEP will be included as clusters. Assuming between 500 and 1000 PrEP-eligible women reached by the TB HIV Care PrEP programme per geographic region annually, we considered a coefficient of variation (CV) ranging from 0.25 to 0.4, and a minimum improvement in uptake of 10 percentage points (5% to 15%). With a conservative CV of 0.4, 5 clusters per arm will provide 87% power to detect this difference at an  $\alpha=0.05$  level of significance. For the second layer of randomization for enhanced social influence activities, a total of 216 wards (a smaller unit of subdivision used in South Africa to divide regions for political and administrative purposes) exist across the 5 intervention sites, which will be randomized across four sub-arms. There will be roughly 54 wards per sub-arm each with at least 10 PrEP-eligible women. Overall, arm 2 is hypothesized to have PrEP initiations of 15% where the least effective sub-arm [no additional enhancement] has an uptake rate of ~10% and the most effective sub-arm [2d which combines PrEP champions and PrEP community mobilization will have] will have an uptake rate of up to ~20%. Having at least 30 venues per sub-arm would provide 84% power, at a 5% level of significance, assuming a conservatively high CV of 0.4, to detect this difference. As this will be an exploratory investigation, the emphasis will be on the additional yield by the enhancements and thus no correction for the multi-arm hypothesis testing will be conducted.

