#### *C. Statistical Analysis Plan*

Results will be synthesized across the data sources and implementation outcomes, and utilized to assess the reach and effectiveness of social influence campaign strategies. Findings from the review of programme logs, social media metrics, and cross-sectional surveys will be reported. Costing data and ranges of intervention fidelity and penetration parameters will be used to inform programme activities. A comparison of the social influence campaign intervention vs standard of care at achieving PrEP uptake (primary), 1-month PrEP persistence (secondary) and 4-month PrEP persistence (secondary) will be key outcomes. Cluster level proportions of clients within the TB HIV Care PrEP programme who initiate PrEP will be compared between the main study arms using the unpaired t-test after a log-transformation if necessary. A secondary analysis will adjust for residual confounding by age and other individual characteristics through a two-stage logistic regression residuals approach. A similar approach will be used for the secondary outcomes and the comparison between sub-arms within the intervention main arm. Changes in PrEP knowledge, attitudes and social support across intervention and control areas over the two time periods (pre- and post-intervention) will be estimated using a difference in differences approach. Prevalence of PrEP knowledge, attitudes and social support across intervention and control areas over the two time periods (pre- and post-intervention) will be summarized by questions/item. Multivariate analysis will be conducted to generate patterns of responses by theme (e.g. perceptions of PrEP). Changes over time will be analysed using the difference in differences approach that uses suitable regression models (e.g. logistic, linear) to study the effect of time period and study arm, as well as their interaction, on the responses.

Analysis of data will be conducted using STATA Version 15.0.

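### The ward layer is a 2x2 factorial randomised within site, but the analysis plan uses neither the factorial structure nor the site strata, and gives no power for either component alone

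*Combined protocol and SAP*

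**What the plan says.** Section 4 (PrEP Social Influence Campaign CRT) and Table 1 define four ward sub-arms inside Arm 2. At one end, "Wards in Arm 2a will not receive any additional strategies". 2b adds champions and 2c adds mobilization. The fourth option is "d) Training and support for venue-based PrEP champions AND PrEP community mobilization teams". Section 7.A stratifies this ward randomisation by site. The word factorial is not used.

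Section 7.B states: "There will be roughly 54 wards per sub-arm each with at least 10 PrEP-eligible women". It plans on the sub-arm with no enhancement, which "has an uptake rate of ~10"%, and on 2d, which "will have an uptake rate of up to ~20"%, with 15% for Arm 2 overall. It quotes 84% power for that extreme contrast with 30 units per sub-arm and a CV of 0.4. It calls the layer exploratory, declines multiplicity correction for multi-arm testing, and says that "the emphasis will be on the additional yield by the enhancements".

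The analysis is one clause in Section 7.C: "A similar approach will be used for the secondary outcomes and the comparison between sub-arms within the intervention main arm". The approach meant is the unpaired t-test on cluster-level proportions, with a secondary two-stage adjustment for age and other individual characteristics. No list of contrasts, component term, interaction or site term is given.

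**The concern.** The programme would want to know whether champions add anything and whether mobilization adds anything. The components are recruited, trained and supported differently, and Section 7.C intends costing data to inform programme activities. The one contrast that has a power figure, 2d against 2a, cannot separate them.

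Read in the most natural way, a comparison between sub-arms tests one component on 54 wards against 54. In a factorial layout all 216 wards inform each component, 108 against 108. An unpaired t-test also leaves out the site strata used in the randomisation. The risk is an imprecise answer on each component from data that could give a sharper one, and a choice of contrasts made after the results are seen.

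**Working it through.** **Inputs (Section 7.B unless noted).** 216 wards, 54 per sub-arm; m = 10 women per ward, a stated minimum; k = CV = 0.4; 2a = 10%, 2d = 20%, Arm 2 overall = 15%; alpha 5%, taken as two-sided. The plan's power sentence counts venues; I apply it to wards, the unit randomised.

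**Rates for 2b and 2c (not stated).** With equal cells, (10 + 2b + 2c + 20)/4 = 15, so 2b + 2c = 30%. The additive interaction is then 20 − 30 + 10 = 0. The equal split, 15% each, is my assumption.

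**Formula (Hayes and Moulton, unmatched clusters).** Variance of one ward proportion: v(p) = p(1−p)/m + k²p². Power = Φ(√[(c−1)(p1−p0)²/(v(p0)+v(p1))] − 1.96).
At m = 10: v(0.10) = 0.01060, v(0.15) = 0.01635, v(0.20) = 0.02240.

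**1. The plan's own figures.**
- Sub-arms, c = 30, 10% vs 20%: √(29 × 0.01/0.0330) = 2.964, power 84.2% (stated 84%).
- Districts, c = 5, 5% vs 15%, m = 1000: √(4 × 0.01/0.004175) = 3.095, power 87.2% (stated 87%).

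Both reproduce.

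**2. Pairwise contrasts at c = 54.**
- 2d vs 2a: 98.0%.
- One component vs 2a (10% vs 15%): √(53 × 0.0025/0.02695) = 2.217, power 60.2%.
- Both vs one (15% vs 20%): √(53 × 0.0025/0.03875) = 1.849, power 45.6%.

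**3. Main effect of one component.** Estimate = ½[(2b − 2a) + (2d − 2c)] = 5 points. The four cell variances sum to 0.0657, so SE = ½√(0.0657/54) = 0.01744. Then 0.05/0.01744 = 2.867 and power is 81.8%. Treating it as 108 vs 108 wards at 12.5% and 17.5% gives 81.5%.

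**4. Women per ward.** 500 to 1000 women per district per year over 5 districts is 2500 to 5000. Divided by 216 this is 11.6 to 23.1 per ward per year, or 5.8 to 11.6 over the 6 months in which the ward components run (Section 4).

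| m | one component vs 2a | main effect |
|---|---|---|
| 5.8 | 42% | 63% |
| 10 | 60% | 82% |
| 11.6 | 65% | 86% |
| 23.1 | 85% | 97% |

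At m = 10 and CV 0.25 the pair is 66% and 87%. With unequal components (13% and 17%, CV 0.4) it is 29% and 40% for the weaker, 85% and 98% for the stronger.

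**5. Departure from additivity (2a = 10%, 2d = 20%, m = 10, CV 0.4).**

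| 2b = 2c | one component vs 2a | main effect |
|---|---|---|
| 12% | 16% | 86% |
| 15% | 60% | 82% |
| 16.5% | 80% | 80% |
| 17% | 85% | 79% |
| 18% | 92% | 78% |

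**6. Precision of the interaction.** SE = √(0.0657/54) = 0.0349, so the 95% half-width is 1.96 × 0.0349 = 6.8 points. The 17% row above is an interaction of 20 − 34 + 10 = −4 points; power to detect 4 points is about 21%.

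None of these figures allows for site stratification or for contamination between wards.

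**The case against.** A reader might infer that the plan commits to separate pairwise tests and excludes main effects. The text does not support that. A t-test of 108 champion wards against 108 others would also be a similar approach, so the plan is silent on main effects.

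A reader might also call the layer under-powered. The plan declares it exploratory, the district-level primary comparison is untouched, and the one contrast it powers has 98% at 54 wards per sub-arm. Low power for contrasts that the plan never claimed to power is a missed efficiency, not a false statement.

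The estimand can be disputed as well. Additional yield may mean each enhanced sub-arm against social media alone, whereas a main effect averages over the presence of the other component. If 2b and 2c both stayed at 10% and 2d reached 20%, the main-effect test would have 88% power for each component although neither does anything alone. Under modest sub-additivity the pairwise test is the stronger one, and the interaction estimate is too imprecise to settle which case holds.

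All of this stands. It argues for reporting main effects beside the sub-arm contrasts, not in place of them. It does not defend leaving the contrasts unstated or the strata out: exploratory status explains the absence of multiplicity correction, not the absence of a defined analysis.

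**Conclusion.** The concern holds as a gap in specification with an efficiency cost. The design is a site-stratified 2x2 factorial, and the plan names neither the component effects nor the strata in its analysis.

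On the plan's inputs the difference is about 60% against 82%. That rests on 15% in each of 2b and 2c (inferred), on no additive interaction, and on the stated floor of 10 women per ward. It is not a fixed deficit. Both figures move with ward size, and the ordering changes at roughly 16.5% to 17% in 2b and 2c when 2d is 20%. For an exploratory layer this is an inexpensive improvement and does not threaten the primary result.

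**What to change.** Add to Section 7.C, for this exploratory layer, one ward-level model among Arm 2 wards with site strata, a champions term and a mobilization term. Report with it:

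- the four sub-arm means, always;
- the 2a vs 2d contrast and each single component vs 2a;
- the interaction with its 95% confidence interval.

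State in Section 7.B the power for the two main effects, conditional on the assumed rates for 2b and 2c and on women per ward, and say whether the unit in the sub-arm power statement is the venue or the ward.

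The cost is wording: no new wards, data or procedures. The downside is that main effects average over the other component and the interaction is known only to about ±7 points. The text should therefore say that a non-significant interaction is not evidence of additivity, and that the sub-arm means must be read alongside the main effects.

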*Post-intervention:* Using the previously sampled districts, we will repeat the approach of randomly selecting teams to accompany after 1-year of intervention activities. This post-intervention survey will be identical in approach to the first survey (n=100 participants per site), although a few additional questions will be added to the post-intervention to assess exposure to the intervention. Participants who completed the first survey will not be intentionally recruited for the follow-on post-intervention survey, but if present and systematically approached on the day of enrollment, individuals will not be excluded if they participated in the prior round of research.

*Pre and post-intervention survey:* The survey will collect minimal individual behavior data, and is mainly intended to assess PrEP knowledge and attitudes, exposure to PrEP promotion events and the social media campaign, as well as the woman or adolescent girl's views on partner, family and peer perceptions of PrEP. Interviews will be conducted cross-sectionally at two time points (serial cross-sectional interviews with programme users). Following screening and the informed consent/assent process, the trained research assistants will administer the survey to study participants on a tablet, reading each question aloud and recording all participant responses. Overall, 600 women and adolescent girls (300 in the standard of care and 300 in the intervention sites) will be enrolled pre-intervention and 600 women and adolescent girls (300 in the standard of care and 300 in the intervention sites) will be enrolled post-intervention, totaling 1,200 participants across the sites and the two time periods.

**For passive enrollment using programme data:** No individual human subjects will be recruited for this element of the study. Rather than individually target programme users with the enhancements to understand their impact, these are strategies that are attempting to change the

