**Cross-sectional survey:** In order to assess the penetration of exposure to the intervention and thus yield insights into the mechanism of intervention effect (or lack thereof), we are assessing changes in PrEP knowledge and community attitudes over time. Given that awareness to PrEP and attitudes may change over time independent of the intervention, we have included both intervention and control sites pre- and post- intervention in order to compare differences in awareness and attitudes over time between the intervention and control sites. Cross-sectional surveys will be administered across 3 intervention and 3 control sites pre- and post-CRT implementation. With 100 surveys being conducted per site per timepoint, we will collect a total of 1200 survey responses across the 6 selected sites (600 pre-intervention and 600 post-intervention). When selecting the 6 sites for survey implementation, programme type (FSW vs. AGYW vs. both) will be accounted for and from there a random sample will be drawn. With 100 women included per site, there will be a sufficient number of women to account for heterogeneity across sites and will ensure sufficient representation across both intervention and control sites, but will also allow for 300 combined FSW/AGYW before and 300 combined FSW/AGYW after intervention in the intervention arms, which will allow for further assessment of the impact of the additional layered strategies (PrEP champions and community mobilization) on modifying the effect of the social media campaign on PrEP uptake.

**Social media metrics:** No sampling plan needed; these will be process indicators used to evaluate engagement with the social media campaign (intervention activities).

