#### *D. Analysis Plan for Implementation Outcomes*

Process and implementation outcomes will be summarized using descriptive statistics across sites. Further, analyses of the primary outcome (PrEP uptake) and secondary outcomes (persistence/retention on PrEP at 1-month and 4-months within the programme) will be evaluated in conjunction with the implementation outcomes to determine the extent to which process outcomes moderate (effect measure modification) the impact of the intervention.

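### The survey difference-in-differences does not say how district-level change enters the error or which degrees of freedom apply, with only 3 districts per arm

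*Combined protocol and SAP*

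**What the plan says.** - **Design.** Section 7.A randomises 10 districts, 5 to each arm. Section 5.C samples 3 districts per arm for the survey and returns to them for the second round: "Using the previously sampled districts, we will repeat the approach of randomly selecting teams to accompany after 1-year of intervention activities". Each site contributes 100 women per round.
- **Survey analysis.** Section 7.C specifies a difference-in-differences analysis that "uses suitable regression models (e.g. logistic, linear) to study the effect of time period and study arm, as well as their interaction". It names no district term, clustered variance, cluster summary or degrees of freedom.
- **Uptake analysis.** The same section is explicit for the primary outcome: "Cluster level proportions of clients within the TB HIV Care PrEP programme who initiate PrEP will be compared" between arms by an unpaired t-test. It then adds: "A similar approach will be used for the secondary outcomes and the comparison between sub-arms within the intervention main arm".
- **Which outcomes are secondary.** Section 4 says "Secondary outcomes will be differences in knowledge, attitudes and peer influence across arms", together with 1- and 4-month sustained use. Section 7.C applies the label only to 1- and 4-month persistence, and section 7.D refers to "secondary outcomes (persistence/retention on PrEP at 1-month and 4-months within the programme".
- **Survey size.** Section 7.B states: "With 100 women included per site, there will be a sufficient number of women to account for heterogeneity across sites". It also notes that "attitudes may change over time independent of the intervention", which is its reason for surveying control sites as well.

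**The concern.** The campaign is delivered to whole districts, so the arm contrast in the survey is a comparison of 3 districts with 3 districts. The written model has arm, period and their interaction, and is silent on the district. Two analysts could follow section 7.C in good faith and reach very different intervals, one from 1,200 separate responses and the other from 6 district changes.

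The survey is meant to explain why the campaign did or did not work. Section 7.B expects attitudes to drift for reasons unrelated to the campaign, and nothing in the plan makes that drift equal across districts. Under an independence analysis, a local shift in one or two districts during the year could be reported as a campaign effect on knowledge or norms.

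**Working it through.** **Inputs from the documents.** 3 districts per arm, 100 women per site per round, the same districts twice. The stated total reproduces: 6 × 100 × 2 = 1,200. No power, prevalence, intraclass correlation or effect size is stated for the survey.

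**Assumptions.** Prevalence p = 50%; no true effect; SD = standard deviation, across districts, of the true pre-to-post change, in percentage points.

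**Step 1: standard error.** The sampling variance of one district's change is 2 × 0.25/100 = 0.005, or (7.07 points)². With 3 districts per arm:

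SE = √[(0.005 + SD²) × 2/3]

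This gives 5.77, 7.07 and 8.16 points at SD 0, 5 and 7.1. The independence analysis always uses 5.77, a 95% half-width of 1.96 × 5.77 = 11.3 points.

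**Step 2: type I error under independence.** Approximately 2[1 − Φ(1.96 × 7.07/√(7.07² + SD²))], with SD in points. The simulation used 200,000 runs per setting.

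| SD of district change (points) | Formula | Simulation, independent responses | Simulation, t-test on 6 changes |
|---|---|---|---|
| 0 | 5.0% | 5.3% | 5.1% |
| 3 | 7.1% | 7.6% | 5.1% |
| 5 | 11.0% | 11.4% | 5.0% |
| 7.1 | 16.6% | 17.3% | 5.1% |
| 10 | 25.8% | 26.3% | 5.0% |

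Logistic and linear versions agree. The formula reaches 10% at an SD of about 4.6 points. An SD of 7.1 corresponds to district-by-period effects of 5 points in each round (5 × √2). At 30% prevalence the simulated figures are similar: 5.0, 7.6, 12.1 and 28.8% at SD 0, 3, 5 and 10.

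**Step 3: stable differences are harmless.** With stable district SDs of 5, 10 and 15 points and no district-specific change, the independence analysis gives 5.3, 4.9 and 4.4%.

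**Step 4: a routine cluster-robust variance.** Let S be the within-arm sum of squared deviations of the 6 changes. The t-test variance is (S/4) × (2/3) = S/6. The robust variance with the usual 6/5 factor is (S/9) × (6/5) = S/7.5. The ratio is 0.8, so the robust standard error is √0.8 = 0.894 of the correct one. Testing at 1.96 is then testing a 4-df t statistic at 1.96 × 0.894 = 1.75, a type I error of about 15%. With t on 5 df the cut-off is 2.571 × 0.894 = 2.30, about 8%. Simulation agrees, whatever the SD.

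**Step 5: price of the cluster-level interval.** The expected 95% half-width on 4 df is 2.776 × 0.940 × SE, where 0.940 is the mean ratio of estimated to true SD on 4 df. That is 15.1 points at SD 0 and 18.5 at SD 5, against 11.3 under independence.

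**The case against.** The plan nowhere says that responses will be treated as independent. A reader might infer that it does, but the model sentence leaves the choice of regression open and lists only the fixed terms. The carry-over sentence can be read to cover the survey, since section 4 lists knowledge, attitudes and peer influence among the secondary outcomes. Section 7.C cites a cluster-trial text, and section 7.A puts a specialist in cluster trials in charge of randomisation. All of that stands, so this is an under-specification and not a demonstrated error. It does not settle the matter: sections 7.C and 7.D call only persistence secondary, and the survey then receives its own regression. Nor would adding some clustered variance be enough, as step 4 shows.

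A reader might also take the statement about 100 women per site to be wrong. It is a sampling rationale about coverage and representation and makes no explicit claim about the error of the arm contrast. It is incomplete for that purpose, not false.

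The size of the problem rests on assumed values, and if districts change alike there is almost none. That stands too. Two further points are fair. Programme type is considered when survey districts are chosen, and an analysis adjusting for it at district level would leave fewer than 4 df. Women are recruited in team-days, which the figures above ignore; the t-test on district changes absorbs that extra variation, whereas an independence analysis does not.

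**Conclusion.** The point holds as a gap in the survey analysis that should be closed before the data are analysed. If the named model is fitted to independent responses and districts change differently between rounds, nominal 95% intervals are too narrow. Type I error is then about 5, 8, 11, 17 and 26% at a district-change SD of 0, 3, 5, 7.1 and 10 points, for 50% prevalence. The documents supply neither the SD nor the prevalence, so this is a range and not a prediction. The result that does not depend on the SD is that routine cluster-robust errors stay at about 15% or 8% with 6 districts, while the t-test on district changes stays at 5%.

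A reader might extend the concern to the trial's main result. The documents do not support that: uptake is compared by a t-test on cluster-level proportions. The consequence is confined to the secondary, mechanistic survey outcomes.

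**What to change.** In section 7.C, state that for the survey outcomes the arm contrast is tested, and its interval formed, from the 6 district-level pre-to-post changes by a two-sample t-test on 4 df. State also that this rule governs the survey outcomes, so that the reach of the carry-over sentence is no longer in doubt. The individual-level regression can stay as a descriptive summary, or for covariate adjustment before the cluster-level step. A mixed model with district and district-by-period effects and small-sample df should be a sensitivity analysis only, noted as conservative: a summary-level approximation puts its type I error at about 0.4 to 3% on 4 df over SDs of 0 to 10 points.

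Optionally, add to section 7.B that 100 women per site sets precision within a district and that the arm comparison rests on 3 districts per arm.

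The cost is a few sentences, with no change to design or data collection. The price is precision. If districts in fact change equally, the expected half-width is about 15 points against 11, and power for a true 20-point difference is about 74% against 93%.
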